7.2 Monitoring for Adverse Events

At each visit, after the subject has had the opportunity to spontaneously mention any problems, the Investigator should inquire about AEs by asking the standard questions:

- “Have you had any health problems since your last study visit?”
- “Have there been any changes in the medicines you take since your last study visit?”

Additionally, changes in *any protocol-specific parameters and/or questionnaires* evaluated during the study are to be reviewed by the Investigator. Any untoward (unfavorable and unintended) change in *a protocol-specific parameter or questionnaire response* that is clinically relevant, in the opinion of the Investigator, is to be reported as an AE. These clinically relevant changes will be reported regardless of causality.

7.3 Procedures for Recording and Reporting

AEs are collected from the time of informed consent. Any pre-existing medical conditions or signs/symptoms present in a subject prior to the start of the study (ie, before informed consent is signed) are not considered AEs in the study and should be recorded in the Medical History section of the eCRF.

In addition, temporary lens awareness or visual changes during the fitting process are not considered AEs if the Investigator assesses that the symptom(s) can reasonably resolve within the anticipated adaptation period.

- ADEs or SAEs are documented on the *Serious Adverse Event and Adverse Device Effect* eCRF within 24 hours of the Investigator's or site's awareness.
- Device deficiencies are documented on the *Device Deficiency* eCRF within 24 hours of the Investigator's or site's awareness.
- A printed copy of the completed *Serious Adverse Event and Adverse Device Effect* and/or *Device Deficiency* eCRF must be included with product returns.
- Additional relevant information after initial reporting must be entered into the eCRF as soon as the data become available.
- Document any changes to concomitant medications on the appropriate eCRFs.
- Document all relevant information from Discharge Summary, Autopsy Report,
- Certificate of Death, etc, if applicable, in narrative section of the *Serious Adverse Event and Adverse Device Effect* eCRF.

Note: Should the EDC system become non-operational, the site must complete the appropriate paper *Serious Adverse Event and Adverse Device Effect* and/or *Device Deficiency* Form. The completed form is emailed to the Study Sponsor at [contact] according to the timelines outlined above; however, the reported information must be entered into the EDC system once it becomes operational.

Any AEs and device deficiencies for non-study marketed devices/products will be considered and processed as spontaneous (following the post-market vigilance procedures) and should be communicated to the device's/product's manufacturer as per local requirements.

Study Sponsor representatives may be contacted for any protocol related question.

Further, depending upon the nature of the AE or device deficiency being reported, the Study Sponsor may request copies of applicable portions of the subject's medical records. The Investigator must also report all AEs and device deficiencies that could have led to a SADE according to the requirements of regulatory authorities or IRB/IEC.

Intensity and Causality Assessments

Where appropriate, the Investigator must assess the intensity (severity) of the AE based upon medical judgment with consideration of any subjective symptom(s), as defined below:

Intensity (Severity)

Mild	An AE is mild if the subject is aware of but can easily tolerate the sign or symptom.
Moderate	An AE is moderate if the sign or symptom results in discomfort significant enough to cause interference with the subject's usual activities.
Severe	An AE is severe if the sign or symptom is incapacitating and results in the subject's inability to work or engage in their usual activities.

For every AE in the study, the Investigator must assess the causality (Related or Not Related to the medical device or study procedure). An assessment of causality will also be performed by Study Sponsor utilizing the same definitions, as shown below:

Causality

Related	An AE classified as related may be either definitely related or possibly related where a direct cause and effect relationship with the medical device or study procedure has not been demonstrated, but there is a reasonable possibility that the AE was caused by the medical device or study procedure.
Not Related	An AE classified as not related may either be definitely unrelated or simply unlikely to be related (ie, there are other more likely causes for the AE).

The Study Sponsor will assess the AEs and may upgrade the Investigator's assessment of seriousness and/or causality. The Study Sponsor will notify the Investigator of any AEs that are upgraded from nonserious to serious or from unrelated to related.

7.4 Return product analysis

Alcon products associated with device deficiencies and/or product related AEs should be returned and must include the Complaint # which will be provided by Study Sponsor after the case is entered in the Study Sponsor's Global Product Complaint Management System. These products should be returned to the Sponsor at the end of the study, unless instructed otherwise by the Sponsor.

7.5 Follow-Up of Subjects with Adverse Events

The Investigator is responsible for adequate and safe medical care of subjects during the study and for ensuring that appropriate medical care and relevant follow-up procedures are maintained after the study.

The Investigator should provide the Study Sponsor with any new safety information (which includes new AEs and changes to previously reported AEs) that may affect the safety evaluation of the device. For AEs that are unresolved/ ongoing at time of subject exit from study, any additional information received at follow-up should be documented in the eCRFs up to study completion (ie, database lock).

Any additional data received up to 1 month after subject discontinuation or exit must be documented and available upon the Study Sponsor's request. All complaints received after this time period will be considered and processed as spontaneous and should be communicated to the medical device's manufacturer as per local requirements.

The Investigator should also report complaints on non-Alcon products directly to the manufacturer as per the manufacturer's instructions or local regulatory requirements.

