4.1 Identity of Study Treatments

DESCRIPTION OF TEST AND CONTROL PRODUCTS		
	TEST	CONTROL
Lens	DD T2	MYDAY
Material	[REDACTED]	stenfilcon A
Water Content	51%	54%
Base Curve (mm)	8.3	8.4
Diameter (mm)	14.2	14.2
Rx powers (D) to be available in this study	-1.50 to -4.00 (0.25 steps)	-1.50 to -4.00 (0.25 steps)
Packaging, Labeling, and Supply	
 • Blister foil pack • Foil label includes: 
 - material name and identifier - base curve - diameter - manufacturing protocol number - packing solution - power - lot number - expiration date - content statement - investigational device statement - country of origin. 	
 • Blister foil pack • Commercial foil with Half Over-label 
 - material name - base curve - diameter - packing solution - power - lot number - expiration date - content statement - investigational device statement - country of origin.

	
 - device statement - sponsor information - country of origin. 
 • Provided in boxes of 10 lenses per power per box, identified with the following: 
 - a label stating the protocol number - material identifier - power - an investigational use only statement - tracking number. • Lenses should be stored at room temperature. 	
 • Provided in boxes of 10 lenses per power per box, identified with the following: 
 - a label stating the protocol number - material identifier - power - an investigational use only statement - tracking number. • Lenses should be stored at room temperature. 	
Usage	
 • Wear: 
 ○ Daily Wear ○ Bilateral, Crossover • Replacement period: DD • Exposure: At least 8 hours per day, 5 days per week over the study duration, 6-day (± 1 day) window per product • Lens Care: N/A 		

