4.2 Accountability Procedures

Upon receipt of the study lenses, the Investigator or delegate will conduct an inventory. Designated study staff will provide the study lenses to the subjects in accordance with their randomization schedule. Throughout the study, the Investigator or delegate must maintain records of study treatment dispensation and collection for each subject. This record must be made available to the study monitor for the purposes of verifying the accounting of clinical supplies. Any discrepancies and/or deficiencies between the observed disposition and the written account must be recorded along with an explanation.

It is the Investigator's responsibility to ensure that:

- All study products are accounted for and not used in any unauthorized manner
- All used foils and unused supplies are returned by each subject
- All unused products are available for return to the Study Sponsor, as directed
- Any study lenses associated with a device deficiency or with any product-related adverse event [ie, ADE or SADE] are returned to the Study Sponsor for investigation. Refer to Section 7.3 of this protocol for additional information on the reporting of device deficiencies and AEs and the return of study products associated with these events.

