8 CONFIDENTIALITY, BIAS AND MASKING

8.1 Subject Confidentiality and Methods Used to Minimize Bias

The Investigator must ensure that the subject's anonymity is maintained throughout the course of the study. In particular, the Investigator must keep an enrollment log with

confidential identifying information that corresponds to the subject numbers and initials of each study participant. At the end of the clinical study, the Sponsor will collect a copy of the enrollment log without any identifying subject information. All documents submitted to the Sponsor will identify the subjects exclusively by number and demographic information. No other personally identifying information should be transmitted to the Sponsor.

This study is double-masked with subjects randomized to use both DD T2 and MYDAY (in a randomized sequence) for the duration of the 2-week treatment period. The Investigator,

[REDACTED] and Sponsor personnel (other than site monitors, lead clinical site manager, person responsible for generating the randomization schedule, and unmasked clinical data managers) involved in reporting, obtaining, and/or reviewing the clinical evaluations will be masked to the identity of the contact lens being administered. This level of masking will be maintained throughout the conduct of the study. Unmasking will occur only after all planned study data have been validated, and the database locked. Masked study personnel must avoid seeking information that may compromise masking. Unmasked study personnel must not disseminate information that is potentially unmasking to any masked personnel. The **masked** and **unmasked** site personnel must coordinate all study activities as necessary to protect masking and minimize bias during the trial.

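### Do the complaint-routing and foil-handling rules in Protocol 4.2, 7.4 and 7.5 defeat the Investigator masking promised in 8.1?

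*Protocol*

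**What the plan says.** Protocol 8.1 puts the Investigator first in its list of masked roles, a list that ends with the words "involved in reporting, obtaining, and/or reviewing the clinical evaluations will be masked to the identity of the contact lens being administered". On timing it says "Unmasking will occur only after all planned study data have been validated, and the database locked". The same section recognises both masked and unmasked site personnel. It forbids the unmasked staff to pass on revealing information, tells the masked staff not to look for it, and requires the two groups to coordinate. Section 8.2 adds an exception for breaking the code in the interest of subject safety.

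Three other sections bear on this:

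- **7.5:** "The Investigator should also report complaints on non-Alcon products directly to the manufacturer". The control, MYDAY, is a CooperVision lens.
- **7.4:** "Alcon products associated with device deficiencies and/or product related AEs should be returned". By contrast, 4.2 sends back to the sponsor "Any study lenses associated with a device deficiency or with any product-related adverse event".
- **4.2:** "the Investigator or delegate must maintain records of study treatment dispensation and collection for each subject". It also makes the Investigator responsible for ensuring that "All used foils and unused supplies are returned by each subject". Section 4.1 lists material name and base curve among the label contents of both foils (8.3 mm for the test lens, 8.4 mm for the control) and describes the control pack as "Commercial foil with Half Over-label".

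SAP 1.4 states only that the study is double-masked.

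**The concern.** Read in isolation, 7.5 asks a masked person to sort complaints by manufacturer, which means knowing the lens. In a crossover of two lenses, learning the lens in one period reveals the other. A control-lens complaint in period 1 could therefore unmask the Investigator for period 2 as well. The Investigator judges the causality of every adverse event (7.3) and assigns the category of each device deficiency (7.1), and the primary endpoint is Snellen acuity measured at the site.

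Sections 4.2 and 7.4 also appear to give a site two return rules for a defective control lens, although device deficiencies are a safety endpoint. Finally, 4.2 does not reserve inventory or collection records for unmasked staff, so the Investigator could see foils that identify the lens. If all this happened in practice, the label of double-masking would promise more than the trial delivered.

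**Working it through.** The plan gives no figure to reproduce on this point. The check is to set the sections side by side and ask whether a site can obey all of them at once.

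**7.5 against 8.1.** A conflict needs three things together: that non-Alcon products include the control lens, that the Investigator acts personally, and that the report is made before database lock. The text does not compel all three.

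- *Timing.* The sentence carries no deadline. It closes a section whose preceding paragraph deals with information arriving up to 1 month after a subject's exit, and with later complaints that go to the manufacturer as spontaneous reports. Reporting after lock satisfies it.
- *Person.* Only the Investigator is named, but 8.1 provides unmasked site staff and forbids the Investigator to seek lens identity. A site reading both sections would have the unmasked staff do any forwarding.
- *In-study route.* Under 7.3, a device deficiency goes on its electronic form within 24 hours of the Investigator or site becoming aware of it, and adverse device effects and serious events go on theirs within the same time. Neither rule distinguishes the two study lenses by manufacturer. The trial data therefore do not depend on 7.5.

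**7.4 against 4.2.** Section 4.2 covers every study lens. Section 7.4 covers a subset, the sponsor's own products, and adds a complaint number and a time of return. It does not say that other products stay behind. A site that returns all affected study lenses and attaches the complaint number to the sponsor's lenses meets both rules. Protocol 6.8 builds the deficiency tables and listings from the Device Deficiency Form, not from returned lenses, so the return route does not change the counts by lens.

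**4.2 against 8.1.** Inventory and records fall to the Investigator or a delegate, and dispensing falls to designated staff. The Investigator must ensure that foils come back, which does not require handling or reading them. Step 10 of Visits 1 and 2 pairs the keeping of foils with an instruction to follow the masking procedures. Section 4.2 thus gives a permission, and 8.1 restricts how it may be used.

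**Can the exposure be sized?** One can count foils. With a new lens in each eye on every day of a 5 to 7 day period, 2 × 5 = 10 to 2 × 7 = 14 foils arise per product, and 20 to 28 per subject over both. This shows that foil return is routine. It says nothing about how often a masked assessor sees a foil, which is the quantity that matters. The 5 to 7 days are also the visit window; 4.1 asks for wear on at least 5 days per week. No complaint rate is given.

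**What cannot be seen.** The list of masked roles in 8.1 is blacked out directly after the Investigator, several visit steps are redacted, and the readable text does not say what the half over-label hides. Neither who measures acuity nor whether subjects can read the lens identity from the foils can be settled, and the missing text cannot be counted against the plan.

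**The case for a change.** The best case for a change rests on 7.5. Section 7.3 already deals with non-study marketed products and says so, whereas 7.5 has no such limit. The sentence before it in 7.5 has a time limit and this one has none, so reading it as post-study is an inference. Section 4.2 allows a delegate, while 7.5 names the Investigator alone. The code-break provision in 8.2 concerns subject safety and regulatory reporting, so routine complaints fall outside it. Deficiency categories such as a wrong base curve or a mislabelled pack may draw the Investigator towards the labelled packaging. The repair would be a few words, with no effect on sample size, visits or analysis.

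Much of this stands as criticism of drafting. Section 7.5 should have said whether it includes the control lens before lock, and 7.4 is narrower than 4.2 for no stated reason. It does not stand as proof of a contradiction, because it requires reading 7.5 as though 8.1 were absent. Section 8.1 is the specific rule on masking and supplies both the unmasked staff and the prohibition that settle how 7.5 is carried out. The low cost of a repair does not show a gain: the new words would record a division of tasks that 8.1 already implies.

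**Conclusion.** The concern identifies loose wording, chiefly in 7.5 and secondarily in 7.4, but it does not call for a change. The sections can be followed together, and a site that does so keeps the Investigator masked. The visual acuity analysis against its 0.05 logMAR margin and the descriptive safety summaries are unaffected. No bias has been shown, and its size cannot be estimated from the documents.

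This rests on two assumptions: that sites use the unmasked personnel provided for in 8.1 for tasks that reveal the lens, and that the masking procedures mentioned in the visit steps exist. If the Investigator in fact routed control-lens complaints or read foils during the trial, that would be a departure from 8.1 in conduct, to be recorded as a deviation. The question of subject masking stays open, because it turns on over-label details that are not visible.

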7.6 Pregnancy in the Clinical Study

Women of childbearing potential or women who are pregnant at the time of study entry are not excluded from participation. Pregnancy should be included in the Medical History section of the eCRF when a pregnant woman enters the study or if a woman becomes pregnant during the study. Pregnancy is not reportable as an AE; however, complications may be reportable and will be decided on a case-by-case basis.

8 CONFIDENTIALITY, BIAS AND MASKING

8.1 Subject Confidentiality and Methods Used to Minimize Bias

The Investigator must ensure that the subject's anonymity is maintained throughout the course of the study. In particular, the Investigator must keep an enrollment log with

confidential identifying information that corresponds to the subject numbers and initials of each study participant. At the end of the clinical study, the Sponsor will collect a copy of the enrollment log without any identifying subject information. All documents submitted to the Sponsor will identify the subjects exclusively by number and demographic information. No other personally identifying information should be transmitted to the Sponsor.

This study is double-masked with subjects randomized to use both DD T2 and MYDAY (in a randomized sequence) for the duration of the 2-week treatment period. The Investigator,

[REDACTED] and Sponsor personnel (other than site monitors, lead clinical site manager, person responsible for generating the randomization schedule, and unmasked clinical data managers) involved in reporting, obtaining, and/or reviewing the clinical evaluations will be masked to the identity of the contact lens being administered. This level of masking will be maintained throughout the conduct of the study. Unmasking will occur only after all planned study data have been validated, and the database locked. Masked study personnel must avoid seeking information that may compromise masking. Unmasked study personnel must not disseminate information that is potentially unmasking to any masked personnel. The **masked** and **unmasked** site personnel must coordinate all study activities as necessary to protect masking and minimize bias during the trial.

8.2 Unmasking of the Study Treatment

Masked information on the identity of the assigned medical device should not be disclosed during the study. If the treatment code needs to be broken in the interest of subject safety, the Investigator is encouraged to contact an appropriate Study Sponsor representative prior to unmasking the information if there is sufficient time. Dependent upon the individual circumstances (ie, medical emergency), the code may be broken prior to contact with the Study Sponsor. The Study Sponsor must be informed of all cases in which the code was broken and of the circumstances involved. Additionally, the Study Sponsor may be required to unmask the information in order to fulfill expedited regulatory reporting requirements.

9 DATA HANDLING AND ADMINISTRATIVE REQUIREMENTS

9.1 Completion of Source Documents and Case Report Forms

The nature and location of all source documents will be identified to ensure that original data required to complete the eCRFs exist and are accessible for verification by the site monitor, and all discrepancies shall be appropriately documented via the query resolution process. Study monitors are appointed by the Study Sponsor and are independent of study site staff. If electronic records are maintained, the method of verification must be determined in advance of starting the study.

At a minimum, source documents should include the following information for each subject:

- Subject identification (name, sex, race/ethnicity)
- Documentation of subject eligibility
- Date of informed consent
- Dates of visits
- Documentation that protocol specific procedures were performed
- Results of study parameters, as required by the protocol
- IP accountability records
- Documentation of AEs and other safety parameters (if applicable)
- Records regarding medical histories and the use of concomitant therapies prior to and during the study
- Date of study completion and reason for early discontinuation, if applicable

It is required that the author of an entry in the source documents be identifiable. Direct access to source documentation (medical records) must be allowed for the purpose of verifying that the data recorded on the eCRF are consistent with the original source data.

Only designated individuals may complete the eCRFs. The eCRFs will be submitted at regular intervals following the clinical study visit schedule. It is expected that all data reported will have corresponding entries in the source documents. The Principal Investigator is responsible for reviewing and certifying that the eCRFs are accurate and complete. The only subject identifiers recorded on the eCRFs will be subject number, and subject demographic information.

